4.1 Description of study design

Those patients receiving pasireotide LAR must return to the study center monthly (+/- 7 days) to receive study medication. Drug dispensing information will be collected and adverse events and clinical benefit will be assessed. Patients receiving pasireotide s.c. must return to the study center on a quarterly basis (every 12 weeks +/- 2 weeks) for resupply of study medication. Drug dispensing information will be collected and adverse events and clinical benefit will be assessed. The patient may return to the clinic at any given time as per standard of care or treating physician recommendation; however, only the quarterly study visits will be recorded.

[figure not shown]
At every visit, the investigator is required to confirm that the patient continues to have clinical benefit and may continue receiving study treatment.

All adverse events and serious adverse events will be collected continuously throughout the study. Information on patient pregnancies and pregnancies of pregnant partners will be collected.

The study is expected to remain open for 10 years from FPFV (or until 10-Jun-2023 in the UK). Patients will continue to be treated in this roll-over study until they are no longer benefiting from their pasireotide treatment as judged by the investigator or until one of the discontinuation criteria is met (please refer to [Section 7.1.5](#)). At each visit the Investigator is required to confirm that the patient continues to derive clinical benefit and may continue receiving study treatment.

A patient will reach the end of study when pasireotide treatment is permanently discontinued.

Figure 4-1 Study design

*Note: The starting dose of pasireotide, and any combination treatment given for Cushing's Disease or Acromegaly, should be the same dose as that which the patient was receiving in the parent study at roll over.

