For the management of LFT increase, QT prolongation, and hyperglycemia refer to specific instructions provided in [Appendix 2](#), [Appendix 3](#) and [Appendix 4](#).

14.8 Appendix 8: Dose modification information for patients with metastatic melanoma or metastatic Merkel cell carcinoma receiving pasireotide s.c (from protocol SOM230X2404)

Patients will continue receiving the dose of pasireotide LAR q28 d at the same dose received during the follow-up period (20, 40, 60 or 80 mg).

In case a dose reduction is needed due to toxicity, the dose can be reduced to the immediate lower dose level (from 80 mg q 28 d to 60 mg q 28 d, from 60 mg q 28 d to 40 mg q 28 d, and from 40 mg q 28 d to 20 mg q 28 d) and can be kept at this level if necessary for the duration of the study or until disease progression or death. However, the dose will not be re-escalated once reduced. In case patients receiving 20 mg q 28 d need to reduce the dose further, they should be discontinued from the study. If a patient requires a dose interruption of > 7 consecutive days from the intended day of the scheduled dose, then the patient must be discontinued from the study and only follow up for toxicity defined in (reference **table below**).

When treatment is interrupted or permanently discontinued due to an AE or abnormal laboratory value the patient must be followed at least once a week for 4 weeks, and subsequently in 4-week intervals, until resolution or stabilization of the event, whichever occurs first.

Patients who experience non-laboratory AEs should be evaluated at least once a week following demonstration of the toxicity until a resolution of the toxicity or study treatment completion occurs.

Treatment interruption and treatment discontinuation

Patients experiencing unacceptable toxicity (AE grade 3 or higher) that the investigator considers directly attributable to pasireotide should have their dose reduced or should be withdrawn from the study. (reference **table below**) should be regarded as a guideline for the treatment of patients experiencing Adverse Events which are judged to be drug related. Any deviation from these guidelines should be discussed and approved by the sponsor.

Adverse events are described as mild (Grade 1), moderate (Grade 2), severe (Grade 3) or life-threatening (Grade 4). Guidelines for treatment of patients experiencing adverse events are indicated below (reference **table below**).

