Table 14-9 Dose modification for AEs, excluding LFT increase, QT prolongation and hyperglycemia for patients from protocol SOM230X2402

Patients	Adverse event	Action
All	AE grade \leq 2 (mild to moderate)	No drug adjustments
	AE grade \geq 3 (severe to life-threatening) and judged as drug related**	
Reduce dose by 20 mg q 28 d to the next dose level as described above in this appendix (Appendix 8).
 
Once the dose is reduced, the patient will stay on the lowered dose for the entire duration of the roll-over
 
If AE recurs at grade \geq 3, reduce dose by 20 mg q 28 d again and remain at lower dose. If AE does not improve to grade \leq 2 the dose is to be reduced further (following the guidance as described above in this appendix (Appendix 8)). If the AE does not improve to grade \leq 2 on the minimum dose (20 mg q 28 d), patient is to discontinue treatment and followed for safety.

For the management of LFT increase, QT prolongation, and hyperglycemia refer to specific instructions provided in [Appendix 2](#), [Appendix 3](#) and [Appendix 4](#). For management of diarrhea, please refer to (reference below section)

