Persisting diarrhea grade 3 or 4 may be treated with hospitalization, high dose loperamide (initial 4 mg, then 2 mg every 2 hours) and addition of opium tincture or dihydrocodeine tartrate tablets/injections, start of *i.v.* fluids and antibiotics as needed with monitoring of patients condition (to rule out dehydration, sepsis, ileus) medical check and workup (perform appropriate additional testing). Observe patient for response.

After 12-24 hours:**Diarrhea resolved**

- Continue instructions for dietary modification
- Gradually add solid foods to diet
- Discontinue loperamide and/or other treatment after 12-hours diarrhea-free interval

Diarrhea unresolved

- If diarrhea still persisting (NCI CTC grades 1 and 2), after 2x 24 hours with high dose loperamide and opiates then admit to hospital and employ measures as for grade 3 and 4 until diarrhea resolved
- If diarrhea still persisting and progressed to NCI grades 3 and 4, employ measures described below.

Treatment of diarrhea grade 3 or 4

Severe diarrhea grade 3 or 4 may be treated with hospitalization, high dose loperamide (initial 4 mg, then 2 mg every 2 hours and addition of opium tincture or dihydrocodeine tartrate tablets/injections, start of *i.v.* fluids and antibiotics as needed with monitoring of patients condition (to rule out dehydration, sepsis, ileus) medical check and workup (see section Diarrhea workup and additional test in the particular trial protocol). Observe patient for response.

After 12-24 hours:

- If diarrhea persisting administer s.c. Sandostatin/octreotide (100-500 µg tid)

- Continue IV fluids and antibiotics as needed
- If diarrhea grade 3 or 4 still persists patients should receive opium tincture or dihydrocodeine tartrate injections s.c. or i.m.
- If diarrhea grade 3 or 4 is still persisting s.c. Sandostatin/octreotide (500-1000 µg tid) should be administered.
- To control and/or resolve diarrhea, next cycle of treatment should be delayed by 1 or 2 weeks. Treatment should be continued only when diarrhea resolved.

Diarrhea workup

Perform appropriate tests ([Fine and Schiller 1999](#)).

Spot stool analysis

- Collect stool separating it from urine (special containers, analysis immediately, exceptionally freeze samples)
- Blood
- Fecal leukocytes (Wright's staining and microscopy) or
- Clostridium difficile toxin

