CTCAE grade ≥ 3 and assessed as study drug related	
Reduce pasireotide to the next lower dose level.
 
• If the AE improves to grade ≤ 2 before the next administration, increase dose back to the prior dose.• If the dose is increased and the AE recurs at a grade ≥ 3, the dose should be reduced again. The patient should stay on this lower dose and no further dose titrations are allowed.• If the AE does not improve to grade ≤ 2, the dose is to be reduced further. If the AE does not improve to grade ≤ 2 on the minimum study dose, the treatment should be stopped.

For the management of LFT increase, QT prolongation, and hyperglycemia refer to specific instructions provided in [Appendix 2](#), [Appendix 3](#) and [Appendix 4](#).

14.10 Appendix 10: Dose modification information for patients with neuroendocrine tumors receiving pasireotide LAR (from protocol SOM230D2101)

Patients continuing into the roll-over study will receive the same dose of pasireotide LAR every 28 days as the last dose administered during the parent study.

When treatment is interrupted or permanently discontinued due to an AE or abnormal laboratory value the patient must be followed at least once a week for 8 weeks, and subsequently in 4-week intervals, until resolution or stabilization of the event, whichever comes first. If a patient requires a dose delay of > 21 days from the intended day of the scheduled dose, then the patient must be discontinued from the study. However, the patient will be followed up for toxicity as previously described. All patients will be followed for adverse events and serious adverse events for at least 56 days following the last dose of pasireotide LAR treatment.

Table 14-11 outlines the follow-up required for toxicities of specific types and CTCAE grades.

Table 14-11 Follow-up evaluations for selected toxicities

Toxicity	Follow-up evaluation
Hematology	If \geq CTCAE grade 3 neutropenia or \geq CTCAE grade 3 thrombocytopenia have been demonstrated, these parameters must be repeated at least twice a week until resolution to \leq CTCAE grade 1 to allow for initiation of re-treatment, and then at least weekly until either initiation of retreatment or until stabilization.

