Persisting diarrhea grade 3 or 4 may be treated with hospitalization, high dose loperamide (initial 4 mg, then 2 mg every 2 hours) and addition of opium tincture or dihydrocodeine tartrate tablets/injections, start of *i.v.* fluids and antibiotics as needed with monitoring of patients condition (to rule out dehydration, sepsis, ileus) medical check and workup (perform appropriate additional testing). Observe patient for response.

After 12-24 hours:**Diarrhea resolved**

- Continue instructions for dietary modification
- Gradually add solid foods to diet
- Discontinue loperamide and/or other treatment after 12-hours diarrhea-free interval

Diarrhea unresolved

- If diarrhea still persisting (NCI CTC grades 1 and 2), after 2x 24 hours with high dose loperamide and opiates then admit to hospital and employ measures as for grade 3 and 4 until diarrhea resolved
- If diarrhea still persisting and progressed to NCI grades 3 and 4, employ measures described below.

Treatment of diarrhea grade 3 or 4

Severe diarrhea grade 3 or 4 may be treated with hospitalization, high dose loperamide (initial 4 mg, then 2 mg every 2 hours and addition of opium tincture or dihydrocodeine tartrate tablets/injections, start of *i.v.* fluids and antibiotics as needed with monitoring of patients condition (to rule out dehydration, sepsis, ileus) medical check and workup (see section Diarrhea workup and additional test in the particular trial protocol). Observe patient for response.

After 12-24 hours:

- If diarrhea persisting administer s.c. Sandostatin/octreotide (100-500 µg tid)

- Continue IV fluids and antibiotics as needed
- If diarrhea grade 3 or 4 still persists patients should receive opium tincture or dihydrocodeine tartrate injections s.c. or i.m.
- If diarrhea grade 3 or 4 is still persisting s.c. Sandostatin/octreotide (500-1000 µg tid) should be administered.
- To control and/or resolve diarrhea, next cycle of treatment should be delayed by 1 or 2 weeks. Treatment should be continued only when diarrhea resolved.

Diarrhea workup

Perform appropriate tests ([Fine and Schiller 1999](#)).

Spot stool analysis

- Collect stool separating it from urine (special containers, analysis immediately, exceptionally freeze samples)
- Blood
- Fecal leukocytes (Wright's staining and microscopy) or
- Clostridium difficile toxin

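### Appendix 8 both ends and continues study treatment after a two-week delay for diarrhoea; the two passages must be reconciled.

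*Protocol*

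**What the plan says.** **Interruption limit.** Appendix 8 (Section 14.8) sets this limit: "a dose interruption of > 7 consecutive days from the intended day of the scheduled dose, then the patient must be discontinued". No cause of interruption is exempted.

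**Diarrhoea.** Below Table 14-9 the appendix adds: "For management of diarrhea, please refer to (reference below section". That section is 14.8.1. Its measures under "Treatment of diarrhea grade 3 or 4" end with the instruction that the "next cycle of treatment should be delayed by 1 or 2 weeks. Treatment should be continued only when diarrhea resolved". For grade 1 or 2 diarrhoea that persists despite high-dose loperamide and opiates, 14.8.1 says to "admit to hospital and employ measures as for grade 3 and 4 until diarrhea resolved".

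**Comparison text.** Section 14.10.3, in Appendix 10, carries the same delay instruction ("next cycle of treatment should be delayed by 1 or 2 weeks"). Discontinuation in Appendix 10 is triggered later: "If a patient requires a dose delay of > 21 days from the intended day of the scheduled dose".

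**Hyperglycaemia (secondary).** Section 7.1.5.1 lists consistent FPG of at least 240 mg/dL, or HbA1c of at least 10%, despite diabetes management. Appendix 4 repeats these thresholds and cites 7.1.5.1, but adds a reference to reduction of the study drug dose.

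**The concern.** The interruption limit and the diarrhoea guidance sit in one appendix, apply to the same patients and concern the same event, a late injection. If the injection is held for two weeks and the diarrhoea resolves, a site can withdraw the patient under one sentence or resume dosing under the other, and cite the protocol either way. Patient safety, time on treatment and exposure are at stake.

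The secondary point is milder. The words added in Appendix 4 can be read as making a prior dose reduction a condition for stopping, which 7.1.5.1 does not require. The protocol's clinical safety section calls hyperglycaemia the most important side effect, so the two texts should read alike.

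**Working it through.** There is no sample size, power or alpha to reproduce, since no hypothesis is tested. The check compares days against limits and then sets the texts side by side.

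**Inputs**
- Appendix 8 limit: discontinue if the interruption exceeds 7 consecutive days from the intended dosing day.
- Section 14.8.1 delay: 1 or 2 weeks.
- Appendix 10 limit: discontinue if the delay exceeds 21 days. Section 14.10.3 delay: 1 or 2 weeks.

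**Rule:** the discontinuation sentence applies if 7 × (weeks of delay) > limit in days.

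| Appendix | Delay | Days | Limit | Discontinuation sentence applies? | Diarrhoea text |
|---|---|---|---|---|---|
| 8 | 1 week | 7 | > 7 | No (7 is not > 7) | continue once resolved |
| 8 | 2 weeks | 14 | > 7 | **Yes** (14 − 7 = 7 days over) | **continue once resolved** |
| 10 | 1 week | 7 | > 21 | No | continue once resolved |
| 10 | 2 weeks | 14 | > 21 | No (21 − 14 = 7 days inside) | continue once resolved |

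Only the two-week option in Appendix 8 conflicts. By implication, so does any delay of 8 to 14 days.

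**Does anything else settle it?**
- Table 14-9 makes no drug adjustment at grade 2 or below and reduces the dose for drug-related events of grade 3 or above. It has no delay rule.
- Section 7.1.5.1 has hepatic, QT and hyperglycaemia criteria but none on length of delay.
- Section 6.2 leaves dose changes to the investigator and refers to the appendices for guidelines.

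**Hyperglycaemia wording.** The thresholds agree in both places (240 mg/dL; 10%). In Appendix 4, if the phrase about being with or without optimal therapy also covers the dose reduction, the two texts match. If the dose reduction is a condition, a patient above threshold with no earlier reduction meets 7.1.5.1 but not yet Appendix 4. On that reading, FPG from 240 up to and including 250 mg/dL meets the stopping threshold but not Appendix 4's own dose-reduction trigger, which is above 250 mg/dL. Section 7.1.5.1 is also not uniform: one sentence says these criteria may require discontinuation, and the next says that medication should stop immediately.

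**The case against.** **A mandatory rule outranks guidance.** The 7-day sentence uses must. Section 14.8.1 is headed as guidance, uses should, and words continuation as a restriction. A careful site might therefore treat the 7-day limit as controlling. The difference in wording is real, but no precedence is stated. Even on this view, 14.8.1 names a delay after which the same appendix does not let the patient continue.

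**The sponsor can approve an exception.** Appendix 8 does mention sponsor approval of deviations, but that sentence concerns its adverse event table, not the 7-day limit. Section 12 says that no authorized deviations are permitted.

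**Few patients, little time.** SAP Table 2-1 lists X2404 as a parent study, but no enrolment count is given. The amendment log says the study opened on 10-Jun-2013, and Amendment 5 is dated 02-Nov-2021. Ten years from opening leaves about 19 months. This objection stands as a limit on size.

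**Stronger readings that the documents do not support**
- *All persisting grade 1 or 2 diarrhoea is caught.* Section 14.8.1 does send it to the grade 3 and 4 measures, but Table 14-9 makes no drug adjustment at grade 2 or below, so this extension is less clear.
- *The visit window adds evidence.* Section 4.1 says "Those patients receiving pasireotide LAR must return to the study center monthly (+/- 7 days) to receive study medication". A two-week delay gives 28 + 14 = 42 days, past 28 + 7 = 35. But Appendix 10 tolerates up to 28 + 21 = 49 days, and Appendix 7 up to 28 + 28 = 56. Passing the window is therefore not evidence of this conflict.
- *The hyperglycaemia rules contradict each other.* The thresholds are identical, Appendix 4 is titled as recommended guidance and defers to 7.1.5.1, and one natural reading removes the difference. Figure 14-3 is not shown in the text available and could not be checked.
- *SAP deviation D03 cannot be scored.* It can be scored against the hyperglycaemia criteria in 7.1.5.1.

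**Conclusion.** The contradiction in Appendix 8 holds, confined to the two-week option: 14 days against a limit of 7. The one-week option is consistent, and Appendix 10 is not affected. The conclusion rests on reading a delayed cycle as an interruption counted from the intended dosing day, which is how the Appendix 8 limit is framed.

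Its reach is narrow. It concerns only X2404 patients whose injection is held for more than 7 days because of diarrhoea, and that number is unknown and may be zero. A reader might infer that the primary analysis is compromised. It is not: the definition of the AE/SAE endpoint and the Safety Set do not depend on either sentence. The point still merits correction, because it concerns whether a patient stays on study drug.

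The hyperglycaemia wording is a secondary ambiguity, not a demonstrated conflict.

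**What to change.** Reconcile the interruption limit in Appendix 8 with the delay instruction in Section 14.8.1, or state which of them governs. Which clinical rule to keep is for the sponsor's clinical team. In the same amendment, align the hyperglycaemia stopping wording of Section 7.1.5.1 and Appendix 4, including whether a prior dose reduction is a condition and whether discontinuation is permissive or immediate. No change to SAP D03 is needed.

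Under Section 12.1 this takes a written amendment with IRB/IEC/REB approval, and Health Authority approval where required. It adds no procedures and no data. The sponsor should first check whether any X2404 patient is still on treatment, since that decides how urgent the Appendix 8 correction is.

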14.8.1 Guidance for diarrhea management

General recommendations:

- Stop all lactose-containing products, alcohol
- Stop laxatives, bulk fiber (Metamucil, Procter & Gamble), and stool softeners (docusate sodium; Colace, Roberts)
- Drink 8 to 10 large glasses of clear liquids per day (water, Pedialyte (Ross), Gatorade (Quaker), broth)
- Eat frequent small meals (bananas, rice, applesauce, Ensure, toast)
- Stop high-osmolar food supplements such as Ensure Plus and Jevity Plus (with fiber)

It is recommended that patients be provided loperamide tablets. It is mandatory that patients are instructed on the use of loperamide at cycle 1 in order to manage signs or symptoms of diarrhea at home. Patients should be instructed to start oral loperamide (initial administration of 4mg, then 2mg every 4 hours (maximum of 16 mg/day) at the first sign of loose stool or symptoms of abdominal pain. These instructions should be provided at each cycle and the site should ensure that the patient understood the instruction. At the beginning of each cycle, each patient should be specifically questioned regarding any experience of diarrhea or diarrhea related symptoms. If symptoms were experienced, then the site should question the patient regarding the actions taken for these symptoms.

Treatment of diarrhea grade 1 or 2

Diarrhea grade 1 or 2 will be treated with standard loperamide (initial at first administration 4 mg, then 2 mg every 4 hours (maximum of 16 mg/day) or after each unformed stool).

12-24 hours later:**Diarrhea resolved**

- Continue instructions for dietary modification
- Gradually add solid foods to diet
- Discontinue loperamide after 12-hours diarrhea-free interval

Diarrhea unresolved

Persisting diarrhea grade 1 or 2 will be treated with addition of opium tincture or dihydrocodeine tartrate tablets/injections with monitoring of patients condition to rule out dehydration, sepsis, ileus) medical check and selected workup if patient does not need hospitalization (see section Diarrhea workup and additional test in the particular trial protocol). Observe patient for response to antidiarrheal treatment.

Persisting diarrhea grade 3 or 4 may be treated with hospitalization, high dose loperamide (initial 4 mg, then 2 mg every 2 hours) and addition of opium tincture or dihydrocodeine tartrate tablets/injections, start of *i.v.* fluids and antibiotics as needed with monitoring of patients condition (to rule out dehydration, sepsis, ileus) medical check and workup (perform appropriate additional testing). Observe patient for response.

After 12-24 hours:**Diarrhea resolved**

- Continue instructions for dietary modification
- Gradually add solid foods to diet
- Discontinue loperamide and/or other treatment after 12-hours diarrhea-free interval

Diarrhea unresolved

- If diarrhea still persisting (NCI CTC grades 1 and 2), after 2x 24 hours with high dose loperamide and opiates then admit to hospital and employ measures as for grade 3 and 4 until diarrhea resolved
- If diarrhea still persisting and progressed to NCI grades 3 and 4, employ measures described below.

Treatment of diarrhea grade 3 or 4

Severe diarrhea grade 3 or 4 may be treated with hospitalization, high dose loperamide (initial 4 mg, then 2 mg every 2 hours and addition of opium tincture or dihydrocodeine tartrate tablets/injections, start of *i.v.* fluids and antibiotics as needed with monitoring of patients condition (to rule out dehydration, sepsis, ileus) medical check and workup (see section Diarrhea workup and additional test in the particular trial protocol). Observe patient for response.

After 12-24 hours:

- If diarrhea persisting administer s.c. Sandostatin/octreotide (100-500 µg tid)

- Continue IV fluids and antibiotics as needed
- If diarrhea grade 3 or 4 still persists patients should receive opium tincture or dihydrocodeine tartrate injections s.c. or i.m.
- If diarrhea grade 3 or 4 is still persisting s.c. Sandostatin/octreotide (500-1000 µg tid) should be administered.
- To control and/or resolve diarrhea, next cycle of treatment should be delayed by 1 or 2 weeks. Treatment should be continued only when diarrhea resolved.

Diarrhea workup

Perform appropriate tests ([Fine and Schiller 1999](#)).

Spot stool analysis

- Collect stool separating it from urine (special containers, analysis immediately, exceptionally freeze samples)
- Blood
- Fecal leukocytes (Wright's staining and microscopy) or
- Clostridium difficile toxin
- Fecal cultures including *Salmonella* spp., *Campylobacter* spp., *Giardia*, *Entamoeba*, *Cryptosporidium* (which can lead to opportunistic infections in immununosuppressed patients), plus *Shigella* and pathogenic *E. coli* - enterotoxigenic, enterohemorrhagic etc., possibly *Aeromonas*, *Pleisiomonas* (if suspected exposure to contaminated water)

Endoscopic examinations

Endoscopic examinations may be considered **only if absolutely necessary**. The bowel is likely to be fragile with evidence of colitis and thus great care and caution must be exercised in undertaking these invasive procedures.

- Gastroscopy to obtain jejunal fluid - re. bacterial overgrowth for cultures and biopsy of proximal jejunum to assess extent of inflammatory jejunitis
- Sigmoidoscopy - reassessment of colitis

